10.2.2 Other safety topics of interest summaries

The safety topics of interest (or AEs with special monitoring) for the bimekizumab program are:

- Infections (serious, fungal, opportunistic and tuberculosis)
- Malignancies
- Major adverse cardiac events (MACE)
- Neutropenia
- Suicidal Ideation and Behavior
- Inflammatory bowel disease
- Hypersensitivity (including anaphylactic reactions)
- Hepatic events and drug-induced liver injury (DILI)

The analyses produced for the TEAE of special monitoring are based on the specifications described in the Bimekizumab safety topic of interest document version from 26-Mar-2020.

Separate tables will be created to summarize each of the above AEs (except when notified) per 100 subject-years by system organ class, high level term, and PT.

Infections

The summary table for fungal infection will include all TEAEs (serious and non-serious) which code to the High Level Group Term “Fungal infectious disorders”.

Opportunistic infections (including tuberculosis) will be summarized in a stand-alone table and will include all opportunistic infection TEAEs identified as per the UCB-defined search criteria which were adjudicated as opportunistic infections (refer to [Appendix 2](#) for further details on the process for identifying opportunistic infections).

No dedicated table will be produced for serious infections, as there will be identified based on MedDRA classification (SOC “Infections and infestations”) using the “Any SAE” table specified in Section [10.2.1](#).

Fungal infections and opportunistic infections will be listed separately.

Malignancies

Two tables will be created on malignancies:

- one table will display all events in the criteria standardized MedDRA Query (SMQ)= “Malignant or unspecified tumors (SMQ)”,
- and another table will display all events in the criteria SMQ= “Malignant tumors (SMQ)”.

The SMQ search will include all TEAEs which code to a PT included in the Scope=Narrow group within each SMQ.

The output tables will include two different overall incidence rows:

- The first overall incidence row will summarize “Any Malignancy” and this row will summarize the incidence of all AEs flagged for inclusion in the table (using the appropriate SMQ depending on the table), regardless of the HLT it codes to.
- The second overall incidence row will summarize “Any Malignancy excluding non melanotic skin cancers HLT” and this row will summarize the incidence of AEs flagged for inclusion in the table (using the appropriate SMQ depending on the table), excluding those which code to an HLT of “skin neoplasms malignant and unspecified (excl melanoma)”.

All malignancy events will be listed.

Cardiac events

The table on cardiac events will summarize events considered as MACE by the external cardiovascular event adjudication committee.

Extended MACE events will be presented in a separate table and listing. All events which are classified by the adjudication committee as any of the following events types will be considered an extended MACE event:

- Non-Fatal Myocardial Infarction (MI)
- Non-Fatal Stroke: hemorrhagic
- Non-Fatal Stroke: ischemic

- Non-Fatal Stroke: embolic
- Non-Fatal Stroke: undeterminable
- Hospitalization or ER for Unstable Angina with urgent revascularization
- Hospitalization for Heart Failure
- Coronary Revascularization Procedures (eg, percutaneous coronary intervention, coronary artery bypass grafting)
- Urgent Revascularization Procedures (ie, due to symptoms of brain ischemia or pending infarction)
- Death due to Myocardial Infarction (MI)
- Death due to Stroke
- Sudden Cardiac Death
- Other CV Death (eg, heart failure, pulmonary embolism, cardiovascular procedure-related)
- Cardiovascular: Undetermined Cause of Death (ie, cause of death unknown)

A separate table and listing will present the adjudicated cardiovascular events by type. For each cardiovascular event type (24 total), the individual PTs which fall within each event type will be summarized.

Additionally, a listing of all events identified for potential review by the cardiovascular event adjudication committee will be produced. This listing will indicate whether each event was escalated to the committee for formal review/adjudication.

Neutropenia

The table on neutropenia will be based on the following PTs (regardless of seriousness):

- Autoimmune neutropenia
- Band neutrophil count decreased
- Cyclic neutropenia
- Febrile neutropenia
- Idiopathic neutropenia
- Neutropenia
- Neutropenic infection
- Neutropenic sepsis
- Neutrophil count decreased

All neutropenia events will be listed.

Suicidal Ideation and Behavior

An external neuropsychiatric adjudication committee will evaluate potential neuropsychiatric events and determine whether any of those events were associated with suicidal ideation and behavior (SIB). If an event is adjudicated as SIB, further information will be provided. A table

and a listing for SIB events as determined by the adjudication committee will be produced as well as a listing for all events escalated to the committee but which were not adjudicated as a SIB event.

A separate table will present the adjudicated neuropsychiatric events by type. For each neuropsychiatric event type (6 total), the individual PTs which fall within each event type will be summarized. It will include events adjudicated as SIB and events adjudicated as non-suicidal. Note that the event type Suicidal ideation can be classified as either SIB or non-suicidal.

Additionally, a listing of all events identified for potential review by the neuropsychiatric adjudication committee will be produced. This listing will indicate whether each event was escalated to the committee for formal review/adjudication.

Inflammatory bowel disease

An external inflammatory bowel disease (IBD) adjudication committee will evaluate potential IBD events and will classify each one as follows:

- Event Type Code 1: Possible IBD – Crohn’s Disease
- Event Type Code 2: Probable IBD – Crohn’s Disease
- Event Type Code 3: Definite IBD – Crohn’s Disease
- Event Type Code 4: Possible IBD – Ulcerative Colitis
- Event Type Code 5: Probable IBD – Ulcerative Colitis
- Event Type Code 6: Definite IBD – Ulcerative Colitis
- Event Type Code 7: Possible IBD – Unclassified
- Event Type Code 8: Probable IBD – Unclassified
- Event Type Code 9: Definite IBD – Unclassified
- Event Type Code 10: Symptoms not consistent with IBD
- Event Type Code 11: Possible Inflammatory Bowel Disease - Microscopic Colitis
- Event Type Code 12: Probable Inflammatory Bowel Disease - Microscopic Colitis
- Event Type Code 13: Definite Inflammatory Bowel Disease - Microscopic Colitis
- Event Type Code 14: Possible Inflammatory Bowel Disease – no further differentiation possible
- Event Type Code 15: Probable Inflammatory Bowel Disease – no further differentiation possible
- Event Type Code 16: Definite Inflammatory Bowel Disease – no further differentiation possible
- Event Type Code 99: Not enough information to adjudicate

A table for adjudicated definite IBD events (event type codes 1, 2, 3, 4, 5, 6, 7, 8, 9, 11, 12, 13, 14, 15 and 16) as determined by the adjudication committee will be produced. It will summarize events determined by the adjudication committee as definite IBD (event type codes 3, 6, 9, 13, and 16), probable IBD (event type codes 2, 5, 8, 12, and 15) and possible IBD (event type codes

1, 4, 7, 11, and 14). Definite and probable IBD will also be aggregated and summarized. This table will be stratified by study participants with or without a previous medical history of IBD. Previous medical history of IBD will be determined using the information recorded on the Extra-Articular Assessment at Screening CRF page (“Does subject have a history of IBD”).

A separate table will present the adjudicated gastrointestinal events by type. For each gastrointestinal event type (17 total), the individual PTs which fall within each event type will be summarized. It will include events determined by the adjudication committee as definite IBD probable IBD and possible IBD. It will also include events determined as Symptoms not consistent with IBD (event type code 10) and Not enough information to adjudicated (event type code 99).

A listing of all events identified for potential review by the IBD adjudication committee will be produced. This listing will indicate whether each event was escalated to the committee for formal review/adjudication.

A separate table and listing will present the adjudicated IBD events by type. For each IBD event type (event type codes 1 through 16 and 99; 17 total), the individual PTs which fall within each event type will be listed.

A third listing will present the individual diagnostic criteria met for each adjudicated IBD event.

Hypersensitivity (including anaphylactic reactions)

The MedDRA anaphylaxis Algorithm described in [Appendix 1](#) will be used to summarize acute anaphylactic events (reported on the same day as when an injection was administered or one day after). An AE glossary table will also be produced to summarize the MedDRA coding for these events. The glossary table will include the following fields: reported term, PT, LLT, HLT, and SOC.

A separate table will be prepared to summarize hypersensitivity events, identified using the SMQ “Hypersensitivity (SMQ)”. All TEAEs which code to a PT included in the Scope=Narrow search will be included in this table. The analysis will be repeated for serious hypersensitivity reactions. An AE glossary table will also be produced to summarize the MedDRA coding for these events. The glossary table will include the following fields: reported term, PT, LLT, HLT, and SOC.

No separate table will be needed for injection site reactions that will be evaluated based on the table on any TEAE by looking under the HLTs “Administration site reactions NEC” and “Injection site reactions”.

Separate listings will be created for anaphylaxis and hypersensitivity events.

An additional analysis will report the serious hypersensitivity events.

Hepatic events and drug induced liver injury

The table on hepatic events will be created based on the SMQ of “Drug related hepatic disorders - comprehensive search (SMQ)” excluding the two sub-SMQs “Liver neoplasms, benign (incl cysts and polyps) (SMQ)” and “Liver neoplasms, malignant and unspecified (SMQ)”. The SMQ search should include all events which code to a PT included in the Scope=Broad and/or Scope=Narrow, regardless of whether they have been judged as related to study medication or not by the investigator. Hy’s Law cases will be reported separately in a liver function test table (see Section [10.3](#))

Hepatic events (including DILI) will also be listed.

Finally, the incidence of each safety topics of interest occurring in the Double-Blind Treatment Period will be reported in one summary table. The risk difference (bimekizumab minus placebo) associated to each safety event will be calculated, together with the associated 95% confidence interval. These results will also be displayed graphically. For each safety topic of interest, the risk difference (RD) will be derived as follows:

$$RD = \frac{\frac{\text{Number of study participants treated with bimekizumab having the safety event}}{\text{Total number of study participants treated with bimekizumab}} - \frac{\text{Number of study participants treated with placebo having the safety event}}{\text{Total number of study participants treated with placebo}}}{}$$

The lower and upper confidence interval bounds for RD will be calculated as follows:

$$RD - Z_{\alpha/2} * SE (RD), RD + Z_{\alpha/2} * SE (RD)$$

Where $Z_{\alpha/2}$ is the critical value from the standard normal distribution (1.96 for a 95% CI).

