2.3 Study design and conduct

AS0011 is a Phase 3, multicenter, randomized, double-blind, placebo-controlled study. To be eligible to participate in this study, study participants must meet the following key inclusion criteria:

- Adult study participants with a diagnosis of active AS, determined by documented radiologic evidence (x-ray) fulfilling the Modified New York criteria for AS (1984), including at least 3 months of symptoms,
- Age at symptom onset < 45 years old,
- Study participant must have moderate-to-severe active disease as defined by BOTH of the following at screening AND at Baseline:
 - BASDAI ≥ 4 AND Spinal pain ≥ 4 on a 0 to 10 Numeric Rating Scale (NRS) (from BASDAI Item 2)

Study participants treatment assignment will be stratified by prior TNF α inhibitor exposure (yes/no) and region (4 categories).

Detailed study entrance criteria are described in the protocol.

The study consists of the following periods:

- a Screening Period (≥ 14 days to ≤ 35 days),
- a 52-Weeks Treatment Period, consisting of:
 - a 16-Week Double-Blind Treatment Period, and
 - a 36-Week Maintenance Period
- and a Safety Follow-Up (SFU) Period, 20 weeks after the final dose of IMP (for study participants who complete the study and do not enter the open-label extension (OLE) study or for study participants who discontinue early, including those withdrawn from IMP).

The maximum study duration per study participant will be up to 73 weeks. The end of the study is defined as the date of the last visit of the last study participant in the study.

At the end of the Baseline visit, eligible study participants will be randomized in a 2:1 ratio (stratified by region [Asia, Eastern Europe, North America, Western Europe] and prior TNF α inhibitor exposure [yes, no]) to receive one of the two following blinded treatment groups:

- Bimekizumab 160mg sc Q4W,
- Placebo

Study treatment will be administered by unblinded study personnel at the study site.

Approximately 300 study participants are planned to be randomized (200 study participants in bimekizumab treatment group, and 100 study participants in placebo group). Study participants will remain on their allowable background medication through the study conduct.

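### The risk-difference intervals for the safety topics use a Wald formula with an undefined standard error and no rule for sparse counts, so they have zero width at 0 vs 0 events and can mislead at low counts

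*SAP*

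**What the plan says.** Section 10.2.2 ends with a combined display. It states that "the incidence of each safety topics of interest occurring in the Double-Blind Treatment Period will be reported in one summary table". It continues: "The risk difference (bimekizumab minus placebo) associated to each safety event will be calculated, together with the associated 95% confidence interval". A plot is also planned: "These results will also be displayed graphically".

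The risk difference is the crude proportion with the event on bimekizumab minus that on placebo. The limits are introduced by "The lower and upper confidence interval bounds for RD will be calculated as follows" and written as "RD - Z_{\alpha/2} * SE (RD), RD + Z_{\alpha/2} * SE (RD"), and the multiplier "is the critical value from the standard normal distribution (1.96 for a 95% CI").

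That is the whole specification in the SAP. It does not define SE(RD), and it has no continuity correction, no exact or score alternative, and no rule for an arm without events. The same formula serves every topic on the list, from "Major adverse cardiac events (MACE"), malignancies, suicidal ideation and behavior (SIB) and inflammatory bowel disease (IBD) to hypersensitivity and hepatic events.

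Section 2.3 gives the size: "Approximately 300 study participants are planned to be randomized (200 study participants in bimekizumab treatment group, and 100 study participants in placebo group").

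For exposure-adjusted incidence rates (EAIR) within an arm, section 10.2 uses exact Poisson limits.

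**The concern.** The Wald interval relies on a normal approximation to a difference of two proportions. When events are few, the estimated variance is itself unreliable, and when there are none it is zero. Several listed topics could plausibly produce between zero and a handful of events in 300 people over 16 weeks.

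This is the only between-arm estimate with a confidence interval that the SAP specifies for these topics, and it is plotted. Readers will judge each topic by whether its bar crosses zero. A bar of no width suggests certainty where the data say least. A bar that just misses zero on four events suggests a signal that the data do not establish. Leaving the SE undefined adds to this, because two standard choices give opposite answers on the same counts.

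**Working it through.** **Inputs.** n1 = 200 and n2 = 100 (section 2.3); z = 1.96 (section 10.2.2; the exact two-sided 5% value is 1.9600, so the one figure the SAP states is reproduced). Event rates are not in the SAP; I assume 0.1% to 5% per arm.

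**Formulas.**
- Unpooled: SE = √[p1(1−p1)/n1 + p2(1−p2)/n2].
- Pooled: SE = √[p(1−p)(1/n1 + 1/n2)], with p the overall proportion.
- Newcombe combines the Wilson limits of each arm. For 0 events out of n, the Wilson upper limit is z²/(n + z²).

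**0 vs 0.** Both SEs are 0, so Wald gives 0.0 to 0.0. The Wilson upper limits are 3.84/203.84 = 1.88% and 3.84/103.84 = 3.70%, so Newcombe gives -3.70 to 1.88. Miettinen-Nurminen gives -3.71 to 1.89.

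**4 vs 0.** RD = 2.00 points.
- Unpooled: SE = √(0.02 × 0.98/200) = 0.00990; 2.00 ± 1.94 = 0.06 to 3.94, excluding zero.
- Pooled: p = 4/300 = 0.01333; SE = √(0.01333 × 0.98667 × 0.015) = 0.01405; 2.00 ± 2.75 = -0.75 to 4.75, including zero.

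**Other counts (bimekizumab vs placebo; percentage points).**

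| Events | Wald unpooled | Wald pooled | Newcombe | Fisher p |
|---|---|---|---|---|
| 2 vs 0 | -0.38 to 2.38 | -0.95 to 2.95 | -2.77 to 3.57 | 0.554 |
| 3 vs 0 | -0.18 to 3.18 | -0.89 to 3.89 | -2.33 to 4.32 | 0.553 |
| 4 vs 0 | 0.06 to 3.94 | -0.75 to 4.75 | -1.90 to 5.03 | 0.305 |
| 6 vs 0 | 0.64 to 5.36 | -0.36 to 6.36 | -1.04 to 6.39 | 0.184 |
| 7 vs 0 | 0.95 to 6.05 | -0.12 to 7.12 | -0.61 to 7.05 | 0.100 |
| 9 vs 1 | 0.03 to 6.97 | -0.81 to 7.81 | -1.43 to 7.42 | 0.173 |
| 0 vs 3 | -6.34 to 0.34 | -5.39 to -0.61 | -8.45 to -0.27 | 0.036 |

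The last row shows the opposite error: unpooled Wald includes zero where Fisher and Newcombe do not.

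**Chance of excluding zero when the true rates are equal (full binomial enumeration; 0 vs 0 counted as not excluding).**

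| True rate | P(0 vs 0) = (1−rate)^300 | Unpooled | Pooled | Newcombe |
|---|---|---|---|---|
| 0.1% | 74% | 0.01% | 0.4% | 0.01% |
| 0.5% | 22% | 1.2% | 3.4% | 0.6% |
| 1% | 4.9% | 5.6% | 4.2% | 1.7% |
| 2% | 0.2% | 9.0% | 3.9% | 3.0% |
| 5% | 0.0% | 6.1% | 4.7% | 4.3% |

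At 2%, 8.1 of the 9.0 points fall against bimekizumab, a consequence of the 2:1 allocation.

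**Coverage with a true difference.** At 1% vs 0.5%, unpooled Wald covers 90.7% and Newcombe 98.7%. At 2% vs 0.5%, the figures are 92.0% and 98.4%.

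**The case against.** Three stronger readings are tempting, and the SAP does not support them.

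- **That this display is the only placebo-controlled view of these topics.** It is not. Section 10.2 and Table 4-3 provide adverse event tables for the double-blind period with placebo and bimekizumab columns. Section 10.2.2 summarizes most topics per 100 subject-years, and such tables carry exact Poisson limits, which do not collapse at zero events. What stands is narrower: no other between-arm estimate with an interval is specified for these topics.
- **That false exclusion of zero follows from the text as written.** It needs the unpooled SE, which is the usual choice but is not stated. With a pooled SE, 4 to 7 vs 0 all include zero. Nor is false exclusion inflated for the rarest topics: at a 0.5% rate it is 1.2%. There the problem is the zero-width interval.
- **That the intervals are unsound for every topic.** The SAP gives no event rates. Fungal infections, hypersensitivity and broadly searched hepatic events may be common enough for Wald to be adequate.

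It can also be said that the table is descriptive, lies outside the testing hierarchy and carries no decision rule, and that the incidences shown beside the interval make a 0 vs 0 row obvious. That limits the consequence but does not make the interval right. Section 10.2.2 also refers to a separate safety-topics document that is not available here; whether it settles the SE or sparse counts is unknown.

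**Conclusion.** The point holds in limited form. The zero-width interval at 0 vs 0 follows from the stated formula under either usual SE and needs no further assumption. How often it will occur does need one: 74% of trials at a true rate of 0.1% in both arms, 22% at 0.5%. The exclusion of zero from 4 vs 0 events onward (with no placebo events), and the 9.0% false exclusion at equal rates of 2%, hold only with the unpooled SE and only at the planned 200/100. They also assume that topics such as MACE, malignancy, IBD or SIB occur in roughly 0.1% to 2% of participants over 16 weeks. Efficacy conclusions and their type I error are unaffected. The defect is in how a descriptive safety comparison will be read, and it is worth correcting because the specification is both incomplete and unsuited to sparse data.

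**What to change.** Replace the formula with one named score-type interval for all topics, either Miettinen-Nurminen or Newcombe, both available through the RISKDIFF option of PROC FREQ, and delete the reference to SE(RD). Name only one, because they differ near the boundary: at 8 vs 0, Miettinen-Nurminen gives 0.24 to 7.70 and Newcombe -0.19 to 7.69; at 0 vs 2, they give -7.01 to -0.08 and -7.00 to 0.38. Check in programming that limits are produced when neither arm has an event.

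No new data or design change is needed, but the statistical cost should be stated. Intervals are noticeably wider at low counts: at 2 vs 0 the Newcombe width is 3.57 + 2.77 = 6.3 points, against 2.38 + 0.38 = 2.8 for unpooled Wald. They are also conservative, so fewer will exclude zero when an excess is real: at true rates of 2% vs 0.5%, 1.3% of trials with Newcombe against 35% with unpooled Wald. A footnote should say that an interval including zero on so few events does not rule out a difference.

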10.2.3 Extra-Articular Manifestations

A summary table will be presented on study participants having TEAE uveitis. The table will include all events defined by one of the following preferred terms: "Autoimmune uveitis", "Iridocyclitis", "Iritis", "Uveitis". The TEAE will be summarized per 100 subject-years by system organ class, high level term, and PT. The analysis will be stratified by study participants with or without a previous medical history of uveitis at Baseline. Study participants with uveitis at Baseline will be identified as the ones having documented an uveitis in the "Extra-articular Assessments form at Baseline" form ("Does subject have a history of uveitis?").

The analysis will be presented on the overall period as well as on the Double-Blind period.

10.2.4 Impact of COVID-19

To assess the impact of the COVID-19 pandemic on safety, additional summaries and listings will be presented.

For reporting purposes, AEs will be assigned to either Pre-COVID-19, COVID-19 or post-COVID-19 pandemic period by comparing the AE start date (based on imputed date) to the COVID-19 pandemic period start and end dates (Section 3.2.2.2) (AE allocated to a period if it starts during the period):

The following categories of TEAE will be summarized by MedDRA SOC, HLT and PT, including EAIR and EAER:

- All TEAEs by time of onset relative to COVID-19 pandemic period (prior/during/post) by region and overall
- All serious TEAEs by time of onset relative to COVID-19 pandemic period (prior/during/post) by region and overall
- All TEAEs leading to study discontinuation by time of onset relative to COVID-19 pandemic period (prior/during/post) by region and overall
- All TEAEs leading to permanent withdrawal of study medication by time of onset relative to COVID-19 pandemic period (prior/during/post) by region and overall

- All COVID-19 related TEAEs by treatment group, region and overall

COVID-19 related TEAEs will be identified by searching for Preferred Terms “Corona virus infection” and “Coronavirus test positive”. These will include confirmed or suspected COVID-19 infections. All the above table summaries will be produced on the overall period, except for the summary on the COVID-19 related TEAEs that will be produced for all treatment periods.

A separate listing of all COVID-19 related AEs will be presented, where COVID-related AEs are identified as described above.

In addition, all listing of AEs will include a column for COVID-19 relatedness (as defined above) and the time of onset of each AE relative to the COVID-19 pandemic.

For the purpose of calculating EAIR and EAER by COVID-19 pandemic period, the calculation of exposure time at risk presented in Section 10.1.5 will be used. An individual study participant may therefore be counted in the denominator for several COVID-19 pandemic periods dependent on whether the study participant is still considered at risk on the COVID-19 pandemic start and stop dates. In this case time at risk will be calculated separately for each period.

